The evolving understanding of pain physiology in children has led to advancements in multimodal analgesic techniques. Pain management plans encompass a spectrum of interventions ranging from medications, psychological support, and regional anaesthesia. Caudal anaesthesia is one of the most commonly performed regional anaesthesia techniques in paediatrics. A single dose of bupivacaine in the epidural space when accessed through the sacral hiatus provides analgesia for

almost the entirety of the surgical procedure time, but unfortunately, its action is time limited in the postoperative period. ⁽⁸⁾

An ultrasound guided technique has been proven to provide better accuracy and success rate along with decreased puncture rates and increased first puncture success rates compared to a blind caudal block. Transverse and longitudinal views using ultrasound illustrate the sacrococcygeal ligament, the two sacral cornua and the dura mater with epidural space. ^(9, 10)

Erector spinae block is a relatively new technique first described by Forero et al in 2016. Since then, it has been described as an effective block in the paediatric population. It effectively blocks somatic and visceral pain when administered correctly in thoracic or abdominal surgeries, unilaterally or bilaterally. ^(11, 12)

Its analgesic effect appears to be due to injecting local anaesthetic into the interfacial plane between the transversus process and erector spinae accompanied by diffusion into paravertebral and intercostal spaces, where it affects the ventral and dorsal rami of spinal nerves. ^(13, 14)

As the field continues to progress, ongoing research and clinical innovations aim to provide an effective approach to the well-being of young surgical recipients with the most amount of pain control. In this study, we hypothesize that, erector spinae block may be an alternative technique for caudal block for perioperative analgesia in children undergoing lower abdominal surgeries. Our aim will be to compare between erector spinae block and the caudal block to determine which one will provide better postoperative analgesia for a longer duration with fewer side effects.

AIM OF THE WORK

Primary aim: is to evaluate the efficacy of postoperative pain management using the Face, Legs, Activity, Cry, Conceal ability (FLACC) Pain Scale.

Secondary aim:

- Intraoperative haemodynamic changes.
- The time to first rescue analgesic.
- Total postoperative analgesic requirements.
- Parent satisfaction with a 5-point Likert scale questionnaire. ⁽¹⁵⁾
- Number of patients required rescue analgesic postoperatively.
- Time to Modified Aldrete score ≥ 9 . ⁽¹⁶⁾
- PACU stay (min).
- Incidence of any adverse effects.

PATIENTS

After approval of the Medical Ethics Committee of the Faculty of Medicine, Alexandria University. An informed written consent from every patient from parent/caregiver will be done in this study, the current study will be performed in El Shatby University Hospital for children on 60 patients who will be scheduled for elective lower abdominal surgeries under general anaesthesia.

The minimum total hypothesized sample size of 60 eligible study participants will be needed to evaluate the efficacy of postoperative pain management using the Face, Legs, Activity, Cry, Consolability (FLACC) Pain Scale. Taking into consideration an effect size of 20%, significance level of 5% and power of 8-% using Chi Square Test.

This study will be a prospective randomized study. Randomization was done using a computer-generated random numbering of each study patient where even numbers will be group (ESB) and odd numbers will be group (CB). Opaque sealed envelopes will be used and will be opened in the operative theatre by an investigator who will be blinded to the study groups. The parents, children, surgeon, and the investigators who will collect the data after the block will be blinded to the study group. Patients will be randomized into two equal groups:

Group (ESPB): patients will receive bilateral ultrasound guided erector spinae block of dilute solution at dose 0.4 ml/kg of 0.25% bupivacaine between the 10th transversus process and erector spinae muscle on each side, provided that it does not exceed toxic dose of bupivacaine 2.5 mg/kg. ⁽¹⁷⁾

Group (CB): patients will receive ultrasound guided caudal epidural block of dilute solution bupivacaine 0.25% at dose 1ml/kg, provided that it does not exceed toxic dose of bupivacaine 2.5 mg/kg. ⁽¹⁸⁾

Inclusion criteria:

- Age between 2-7 years old.
- ASA I-II.
- Elective surgery under general anaesthesia.
- Lower abdominal surgery.

Exclusion criteria:

- Parent/caregiver refusal.
- Allergy to one of the study medications.
- Renal or cardiac disease.
- Infection or redness at the site of injection.
- Clinically significant coagulopathy.
- Spinal anomalies.
- Altered mental status.
- Developmental delay.
- Additional surgery at different surgical sites.
- Block failure.

METHODS

Preoperative evaluation

1. All patients will be evaluated the day before surgery through proper history taking and clinical examination to exclude cardiovascular, respiratory, neurological, and metabolic diseases.
2. Routine laboratory investigations including:
 - Complete blood count (CBC).
 - Bleeding time.
 - Clotting time.
 - Prothrombin activity & INR.
 - Random blood sugar.
3. All parents will be informed about the techniques of both erector spinae and caudal blocks, and a written consent will be obtained from every parent.
4. All children will not take any solid food for 6 hours preoperatively, but each will be allowed to drink clear fluids up to 2 hours before induction of anaesthesia.

Anaesthetic Technique:

- On arrival to operating theatre, all patients will be attached to a multichannel monitor to display continuous ECG monitoring, non-invasive BP monitoring and peripheral oxygen saturation (SpO₂), nasopharyngeal temperature monitor using Draeger Monitor model Vista 120, Germany.

- Inhalational induction will be conducted using incremental concentrations of sevoflurane up to 8% with 100% O₂ (4 L/min) via face mask (Jackson-Rees modification of Ayer's T-piece).
- After loss of consciousness, a 24G cannula will be inserted into a peripheral vein.
- Laryngeal mask airway (LMA) that is appropriate size to age will be inserted, and anaesthesia will be maintained with oxygen and Isoflurane at double MAC delivered via Jackson-Rees circuit with pressure supported spontaneous ventilation (Trigger Sensitivity 0.7 L/min, PEEP 3, PS 10) using Penlon Ventilator (AV-S Model, Made in UK).
- A diclofenac sodium suppository will be administrated in a dose of 1 mg/kg.
- Bolus intravenous lactated ringers' will be given at the dose of 10 ml/kg.
- No intraoperative muscle relaxants, sedatives, or IV opioids will be administered.

Block Procedure:

All blocks will be given under ultrasound guidance (Philips ClearVue 350 made in USA) using a longitudinal parasagittal transducer probe (6–12 MHz) by the same experienced anaesthesiologist who will not participate in data collection, another anaesthetist will be called to the operating room after preparing the patient and block procedure so that, he will be blinded to group allocation.

Group ESPB:

Patients will be placed in lateral decubitus position. The area at the level of and 1-2 cm lateral to T10 over both sides of spine will be sterilized with 10% povidone-iodine and the probe will be placed in sterile gloves. After visualization of the erector spinae

muscle, the needle will be inserted proximally. After hydro dissection, the needle tip will be confirmed to be between the fascia of the erector spinae muscle group and the transverse process, the dilute solution of bupivacaine 0.25% at dose 0.4 ml/kg will be injected on each side.⁽¹⁶⁾ After the block patients will be placed in supine position and surgery will take place 10 minutes after injection.

Group CB:

After induction of general anaesthesia, the patient will be placed in left lateral decubitus position with the upper hip flexed at 90-degree angle. The needle insertion site will be sterilized using 10% povidone-iodine and the probe will be covered with sterile gloves. The sacral hiatus will be visualized using the ultrasound as two hyperechoic band like lines, the superior line being the sacrococcygeal ligament and the inferior line the dorsum of the pelvic surface of the sacrum. A “pop” or “give” is usually felt when the sacrococcygeal ligament is penetrated. A 22G needle will be introduced at a 45° angle. Cautious aspiration will be performed to rule out an inadvertent systemic or spinal needle location then patients will receive dilute solution of bupivacaine 0.25% at dose 1 ml/kg between the two sacral cornua while observing caudal epidural space dilation or turbulent flow with Doppler. Then, we will wait 10 minutes before the first surgical incision.⁽¹⁸⁾

Haemodynamic will be closely monitored. Failure of block will be defined as increase in heart rate and or mean arterial blood pressure (MAP) above 10% than baseline values at the beginning of surgery, intravenous fentanyl will be given at dose 0.5 ug/kg and patient will be excluded from the study and replaced by another patient. Methods to keep normothermia will be done via warmed iv fluids and forced air-warming blankets.

At the end of surgery, O₂ 100% > 5 L/min will be continued after the discontinuation of sevoflurane. Once the patient shows adequate recovery from anaesthesia, oropharyngeal suction will be performed, and the LMA will be removed. Patients will be transferred to the post anaesthesia care unit (PACU) for monitoring of vital signs. Children will be considered ready for discharge from the PACU when being fully awake, stable vital signs for 30 min, no pain, no nausea or vomiting and the Modified Aldrete post-anesthesia score was ≥ 9 .

MEASUREMENTS

The following parameters will be measured:

1. Demographic data:

- Age.
- Sex.
- Weight.
- **Duration of surgery:** (time from the start of induction till discontinuation of the inhaled anaesthetics in minutes).
- **Duration of anaesthesia:** (from skin incision to final skin sutures in minutes).
- **Type of surgical procedure.**

2. Haemodynamic measurements:

- Heart rate (beats/min) using lead II electrocardiogram (ECG) waves.
- Mean arterial blood pressure: (MABP) in mmHg.
- Oxygen saturation.

They will be monitored and recorded at the following times:

- Pre-induction.
- Post-induction.
- Immediately after performing the block.
- At the start of surgical manipulation.
- Intraoperative every 10 minutes.
- At the end of the operation.

3. Time to Modified Aldrete score ≥ 9 .
4. PACU stay (min).
5. Postoperative pain: It will be assessed 15, 30 minutes in recovery room then every 2 hours the next 8 hours using FLACC Behavioural Pain Assessment Scale. Postoperative pain score will be assessed by a nurse blinded to the patient's anaesthetic management.⁽¹⁹⁾

FLACC Behavioural Pain Assessment Scale 5 parameters: Table (1)

1. Face.
2. Legs.
3. Activity.
4. Cry.
5. Consolability.

Table (1): FLACC Behavioural Pain Assessment Scale

Category	0 score	1 score	2 score
Face	No Particular expression or smile	Occasional grimace or frown; withdrawn, disinterested	Frequent to constant frown, clenched jaw, quivering chin
Legs	Normal position or relaxed	Uneasy, restless, tense	Kicking or legs drawn up
Activity	Lying quietly, normal position, moves easily	Squirming, shifting back and forth, tense	Arched, rigid, or jerking
Cry	No cry (awake or asleep)	Moans or whimpers, occasional complaint	Crying steadily, screams or sobs; frequent complaints
Consolability	Content, relaxed	Reassured by occasional touching, hugging, or being talked to; distractible	Difficult to console or comfort

Interpreting the Behavioural Score: Table (2)

Each category is scored on the 0–2 scale, which results in a total score of 0–10.

Table (2): Interpreting the FLACC Behavioural Score

0	Relaxed and comfortable
1–3	Mild Pain
4–6	Moderate pain
7–10	Severe Pain

6. Time to first postoperative analgesic request

The time elapsed between end of surgery and first administration of an analgesic.

A postoperative pain score of ≥ 4 will be managed with paracetamol 10 mg/kg intravenous then will be repeated every 6 hours as required.

If pain persists after dose of paracetamol or score >4 , nalbuphine will be given at dose 0.1 mg/kg intravenously.

7. Total postoperative analgesics requirement will be recorded.

8. Number of patients who will require postoperative rescue analgesia.

9. Parent satisfaction:

Parent satisfaction with a 5-point Likert scale questionnaire.

10. Side effects:

A) Side effects related to bupivacaine:

- **CNS:** Nausea, vomiting, circumoral numbness, facial tingling, vertigo, tinnitus, restlessness, anxiety, dizziness, seizure, coma.
- **Cardiovascular:** hypotension, arrhythmia, bradycardia, heart block, cardiac arrest.
- **Allergic reactions**

B) Side effects related to the erector spinae technique:

In addition to the common complications associated with any peripheral nerve block (local anaesthetic toxicity, intravascular injection, nerve injury, bleeding, and infection), vascular puncture, pleural puncture, pneumothorax, and failed block are the primary complications.

C) Side effects related to the caudal block technique:

Epidural abscess, meningitis, post dural puncture headache, subdural injection, pneumocephalus, air embolism and back pain.

ETHICS OF RESEARCH

Research on human or human products:

- Prospective study: Informed consent will be taken from patients. In case of incompetent patients, the informed consent will be taken from the guardians.
- Retrospective study: Confidentiality of records will be considered.
- DNA / genomic material: Informed consent for DNA / genomic test and for research will be taken from patients. No further tests will be carried out except with further approval of committee and patients. If the samples will travel outside Egypt the researcher will be responsible for transportation and security approval.
- All drugs used in the research are approved by the Egyptian Ministry of Health.

Research on animal:

- The animal species are appropriate for the test.
- After test, if the animal will suffer, it will be euthanized and properly disposed.

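### The primary FLACC aim fixes no variable, and its chi-square sizing (20% effect, no category or base rate) does not give 60 children on the usual readings

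*Protocol*

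**What the plan says.** In the Protocol, Aim of the Work, the primary aim "is to evaluate the efficacy of postoperative pain management using the Face, Legs, Activity, Cry, Conceal ability (FLACC) Pain Scale". The introduction says the comparison is meant to "determine which one will provide better postoperative analgesia for a longer duration".

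Measurements, item 5, gives the timing: "It will be assessed 15, 30 minutes in recovery room then every 2 hours the next 8 hours". That is two readings in recovery and four at two-hour intervals, six in all. Each reading is a sum of five items, "which results in a total score of 0–10". None of the six is designated primary.

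The sample-size paragraph under Patients says: "The minimum total hypothesized sample size of 60 eligible study participants will be needed" to evaluate pain management on FLACC. The basis follows: "Taking into consideration an effect size of 20%, significance level of 5% and power of 8-% using Chi Square Test".

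The protocol has two sets of FLACC cut-points. Table (2) gives four bands for interpreting the score. Measurements, item 6, gives a rescue trigger: "A postoperative pain score of ≥ 4 will be managed with paracetamol". Neither is linked to the primary aim or to the sizing. One secondary aim is "Number of patients required rescue analgesic postoperatively".

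**The concern.** A chi-square test compares proportions in categories. To size one, the plan must say what the category is, when it is read, and either what rates are expected or what value of w is meant. The paragraph gives only a 20% effect, which could be an absolute difference, a relative difference or Cohen's w. A chi-square on FLACC is possible, for example on scores of 4 or more, but the split and the time are left open.

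Two things are at stake. First, with no variable fixed, any of six time points, several summaries or several cut-offs could be reported as the primary result. Second, if the printed inputs do not lead to 60, the trial may have much less power for the stated effect than the paragraph implies. A non-significant comparison would then be weak evidence on whether the blocks differ.

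**Working it through.** **Inputs from the Protocol.** Total 60 in two equal groups (30 each), effect 20%, significance 5%, chi-square test. The power figure is printed with its second digit missing; I take 80%, the most lenient value from 80 to 89. Sidedness is not stated; I take two-sided and also show one-sided. Base rates are not given; the range below is my assumption.

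**Reading 1: 20% is an absolute difference.** With p̄ the mean of the two rates and d = 0.20,

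n per group = [1.96·√(2p̄(1−p̄)) + 0.8416·√(p₁(1−p₁) + p₂(1−p₂))]² / d².

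- 20% vs 40%: (1.96·√0.42 + 0.8416·√0.40)² / 0.04 = (1.270 + 0.532)² / 0.04 ≈ 81.2, so 82 per group and 164 in total.
- 0% vs 20%: (1.96·√0.18 + 0.8416·√0.16)² / 0.04 = (0.832 + 0.337)² / 0.04 ≈ 34.1, so 35 per group and 70 in total.

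Power at 30 per group is Φ{[d·√30 − 1.96·√(2p̄(1−p̄))] / √(p₁(1−p₁) + p₂(1−p₂))}. For 20% vs 40% this is Φ[(1.095 − 1.270)/0.632] = Φ(−0.276) = 39%. The exact columns enumerate all outcomes of two binomials of size 30.

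| Rates | Total N, formula | Total N, continuity-corrected | Power with 60, formula | Exact, uncorrected | Exact, corrected | Difference detectable with 60 at 80% power (formula) |
|---|---|---|---|---|---|---|
| 0 vs 20% | 70 | 88 | 0.745 | 0.877 | 0.572 | 22 points |
| 5 vs 25% | 98 | 118 | 0.586 | 0.633 | 0.436 | 28 |
| 10 vs 30% | 124 | 144 | 0.490 | 0.499 | 0.372 | 31 |
| 20 vs 40% | 164 | 182 | 0.391 | 0.392 | 0.298 | 34 |
| 30 vs 50% | 186 | 206 | 0.349 | 0.351 | 0.259 | 35 |
| 40 vs 60% | 194 | 214 | 0.338 | 0.350 | 0.257 | 35 |

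The last column applies to the lower rate of each row. The required totals are symmetric: 75% vs 95% needs the same number as 5% vs 25%.

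**Reading 2: 20% is Cohen's w.** For 1 df, N = (1.96 + 0.8416)² / 0.2² = 7.849 / 0.04 = 196.2, so 197. With the four bands of Table (2), 3 df, N = 273. Power with 60 is 34% and 22% respectively.

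**Reading 3: 20% is a relative reduction.** From base rates of 80% down to 30%, the total needed is 246 to 1718.

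**Where 60 does appear.** A one-sided 5% test needs 54 for 0% vs 20%, 60 for 1% vs 21%, 78 for 5% vs 25%, and up to 154. Two-sided, the exact uncorrected test with 60 has 88% power at 0% vs 20% and 82% at 1% vs 21%. All these settings need one group to have almost no events or, by symmetry, almost all children to have the event. The protocol states no such rate. Reading the power as 85% or 89% only raises the totals: the smallest becomes 78 or 88.

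**What 60 deliver for a score.** A t-test with 30 per group has 80% power for 0.736 SD. For a rank-sum test, 0.736/√0.955 = 0.753 SD, using the normal-theory efficiency.

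**If all six readings were tested at 5%.** The chance of at least one false positive is 1 − 0.95⁶ = 26% if they are independent, and 24%, 21% or 16% at assumed equal correlations of 0.3, 0.5 or 0.7 (simulated).

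**The case against.** The best reply is that the protocol gives the instrument, the assessment times, a blinded assessor, severity bands, a threshold of 4 and a test. The per-child summary and the handling of repeated readings are often left to an SAP, which may exist. It can also be said that 60 cannot be called wrong when base rate and sidedness are unstated, because some settings give it.

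The first point has some weight for analysis detail. It does not cover the sizing: the protocol prints a basis for 60, and an SAP written later would not make those inputs yield that number. The second point limits the claim. The number 60 is not impossible, but it is reached only at extreme settings that the protocol does not state.

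Three smaller points stand. The protocol does not plan six separate tests, so the 16% to 26% figure is conditional and shows only why one variable should be fixed. The missing digit in the power may be a slip or a reading fault and is not counted as an error in itself. The rank-sum figure of 0.75 SD assumes roughly normal data, whereas FLACC is a bounded integer score with likely ties.

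**Conclusion.** The concern holds. The primary aim fixes no variable, and the stated sizing cannot be traced to one. At two-sided 5% and 80% power, a 20-point difference needs 98 to 194 children for lower rates of 5% to 40%, and w = 0.2 needs 197. With 60, power for 20 points over that range is 59% down to 34% by formula (63% down to 35% exact, uncorrected), and for w = 0.2 it is 34%. The base rates are assumed, but the conclusion changes only when a rate is within about one point of 0% or 100%, and then only with the uncorrected exact calculation or a one-sided test.

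**What to change.** Before any data are seen, name one primary FLACC variable that suits the aim of longer analgesia. The options are:

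- the score at one stated time point, compared by rank-sum;
- one summary per child, such as the mean or area under the curve to 8 hours, compared by rank-sum or t-test;
- the proportion with FLACC ≥ 4 in a stated window, compared by chi-square.

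Test it once at two-sided 5% and make every other reading, band and cut-off secondary. If the proportion is chosen, say how it differs from the secondary count of children needing rescue, since the same threshold triggers rescue. For any option that uses later readings, say how scores after rescue are handled.

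Keep 60 children and replace the sample-size sentence with what they deliver for that variable at 80% power: about 0.74 SD (t-test) or 0.75 SD (rank-sum) for a score, or about 28 to 35 points for a proportion with a lower rate of 5% to 40%. Justify the SD or base rate from a source, say why a difference of that size is worth detecting, and print the power in full.

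The cost is wording in the aim and the sample-size paragraph, with no new data and no more children. The stated detectable difference becomes less favourable. Any single variable also misses some patterns: a mean over all readings dilutes a difference confined to the late hours, and a single time point misses differences elsewhere. Time to first rescue, already collected, should be reported beside it.

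### The total of 60 does not follow from the stated 20% effect, 5% significance and chi-square test unless one group's rate is close to 0% or 100%

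*Protocol*

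**What the plan says.** The sample-size paragraph in the protocol's PATIENTS section states: "The minimum total hypothesized sample size of 60 eligible study participants will be needed". The purpose given is the evaluation of postoperative pain on the FLACC scale. The inputs follow in one sentence: "Taking into consideration an effect size of 20%, significance level of 5% and power of 8-% using Chi Square Test". Allocation is to two equal groups, so 60 means 30 per arm.

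The paragraph gives no rate in either group, no FLACC cut-off or category, no sidedness and no scale for the 20%. The power is printed as 8-%.

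The rest of the protocol does not fill these gaps. AIM OF THE WORK says: "Primary aim: is to evaluate the efficacy of postoperative pain management", using FLACC, with no cut-off or time point. MEASUREMENTS item 5 describes a scale "which results in a total score of 0–10" and sets out four bands in "Table (2): Interpreting the FLACC Behavioural Score". Item 6 uses a threshold to trigger analgesia: "A postoperative pain score of ≥ 4 will be managed". Neither the bands nor the threshold is linked to the primary aim or to the chi-square calculation.

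**The concern.** The protocol presents 60 as the output of a calculation, so the figure should be recoverable from its inputs. For a chi-square test, the sample size needed for a given difference depends strongly on the underlying rates, and these are absent. A reader who tries ordinary rates gets totals well above 60.

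What is at stake is the meaning of a negative result. The protocol implies that 60 children suffice for a 20% effect. If that effect is 20 percentage points at mid-range rates, a trial of this size would miss it about 61 to 65% of the time. The introduction hypothesises that the erector spinae block may be an alternative to the caudal block, so a non-significant comparison could be read as support for that when the trial simply had little chance of seeing a difference.

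**Working it through.** **Inputs.** From the PATIENTS section: total 60, 1:1, so n = 30 per arm; effect 20%; alpha 0.05; chi-square test. Assumptions: power 80% (printed as 8-%), two-sided test, all 60 analysed. Rates are not given, so a range is shown. Rates mirrored about 50% give the same results.

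**Attempt to reproduce 60: 20-point absolute difference, usual pooled formula.**

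n per arm = [1.960·√(2p̄(1−p̄)) + 0.842·√(p₁(1−p₁) + p₂(1−p₂))]² / (p₂−p₁)²

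- 40 vs 60%: (1.386 + 0.583)² / 0.04 = 96.9, so 97 per arm, total 194.
- 10 vs 30%: (1.109 + 0.461)² / 0.04 = 61.6, so 62 per arm, total 124.
- 0 vs 20%: (0.832 + 0.337)² / 0.04 = 34.1, so 35 per arm, total 70.

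Even at the extreme of 0 vs 20% this formula gives 70, and the unpooled version gives 64. No base rate reproduces 60 with either.

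**Exact check.** The pooled formula is conservative near 0%, so power was also computed by enumerating all pairs of binomial outcomes and applying the uncorrected two-sided chi-square test:

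| Rates | Power at 30 per arm | Total for 80% power (exact) | Total (pooled formula) |
|---|---|---|---|
| 0 vs 20% | 88% | 54 | 70 |
| 1 vs 21% | 82% | 60 | 76 |
| 2 vs 22% | 76% | 66 | 82 |
| 5 vs 25% | 63% | 88 | 98 |
| 10 vs 30% | 50% | 118 | 124 |
| 20 vs 40% | 39% | 160 | 164 |
| 30 vs 50% | 35% | 188 | 186 |
| 40 vs 60% | 35% | 194 | 194 |

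On the exact calculation, power at 30 per arm falls to 80% at a lower rate of about 1.3%.

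**20% relative reduction (exact).**

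| Rates | Total for 80% power | Power at 30 per arm |
|---|---|---|
| 99 vs 79.2% | 60 | 81% |
| 95 vs 76% | 94 | 60% |
| 90 vs 72% | 142 | 43% |
| 80 vs 64% | 244 | 28% |
| 50 vs 40% | 784 | 12% |

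**Cohen's w = 0.20.** With 1 df, N = (1.960 + 0.842)² / 0.20² = 7.849 / 0.04 = 196.2, so 197; power at 60 is 34%. If all four FLACC bands were compared (3 df), N would be 273.

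**What 60 can detect (exact, 80% power, 30 per arm).**

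| Lower rate | Detectable difference (points) |
|---|---|
| 5% | 26 |
| 10% | 30 |
| 20% | 34 |
| 30% | 35 |
| 40% | 35 |
| 50% | 33 |

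For a mean score, a two-sided t-test with 30 per arm detects 0.74 SD.

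**The case against.** The strongest reply is that the inputs are undefined rather than the arithmetic proven wrong. The protocol does not fix the rate, the sidedness or the meaning of the 20%, and 60 is attainable for an absolute or a relative 20% if one rate is extreme. This is true, and it is why no single corrected sample size can be given. It does not rescue the figure: the protocol states no such rate, and the standard pooled and unpooled two-sided formulas miss 60 even at 0%.

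A one-sided test would help somewhat. Exact one-sided power at 30 per arm is 86% at 2 vs 22%, but 76% at 5 vs 25%, 65% at 10 vs 30%, 52% at 20 vs 40% and 45% at 40 vs 60%. The supporting range of lower rates widens to somewhere between 2 and 5%, and ordinary rates remain short. Reading 60 as a per-group number would fit roughly 9 vs 29%, but the protocol says 60 is the total. Reading the damaged power figure as 85 to 89% only raises the requirement.

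Three smaller points stand. Cohen's w is never mentioned, so that reading is only one possibility. The misprinted power may come from text extraction. The protocol plans no equivalence test and asks which block is better, so the misreading of a null result is a risk and not something the plan intends.

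**Conclusion.** The concern holds. With power taken as 80%, a two-sided 5% test, equal arms and 60 analysed, the stated inputs do not yield 60 under the usual readings. For a 20-point difference the shortfall runs from 28 patients (88 against 60, lower rate 5%) to 134 (194 against 60, 40 vs 60%). Equivalently, power is 35 to 63% for lower rates between 40 and 5%, where 80% appears to be claimed. The only route to 60 on a two-sided test is an unstated rate of about 0 to 1% or 99 to 100%, and then only by exact enumeration or a similar method. The intended rate is unknown, so the required size can be ranged but not fixed. A sample size the trial relies on that its own inputs do not support must be corrected.

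**What to change.** Keep 60 and rewrite the sample-size paragraph:

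1. State the power as a legible number (if the source file also shows 8-%) and state the sidedness.
2. Say whether the 20% is an absolute difference, a relative change or a standardised effect.
3. Name the FLACC quantity behind the calculation: a defined category at a defined time with its assumed rate, or a score with its assumed SD.
4. Restate what 60 delivers. For a proportion: 30 per group gives about 80% power, two-sided 5%, for a difference of about 33 to 35 percentage points if the lower rate is 20 to 50%, or about 26 to 30 points if it is 5 to 10%. For a mean score: 30 per group gives 80% power, two-sided 5%, for about 0.74 SD; the named test would then have to change from chi-square.
5. Add one sentence on whether a difference that large is expected between two active blocks, and commit to reporting the group difference with its 95% confidence interval.

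If the assumed rate really is near 0% or 100%, stating it together with the calculation method would support 60.

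The cost is wording in one paragraph, with no extra patients. The drawback is that the stated power or detectable difference becomes less favourable, and 60 may look small for a comparison of two active blocks.

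### Allocation takes no account of the type of operation and the only test named is a plain chi-square; this is valid, but it leaves chance imbalance uncontrolled and gives up a little precision

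*Protocol*

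**What the plan says.** All references are to the protocol; no SAP is at hand.

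- **Eligibility.** Under Inclusion criteria the operation is specified only as "Lower abdominal surgery", elective and under general anaesthesia, in children aged 2-7. There is no list of procedures. The exclusion criteria remove children who have additional surgery at another site.
- **Allocation.** The PATIENTS section describes one computer-generated list, "where even numbers will be group (ESB) and odd numbers will be group (CB", and two equal groups. It mentions neither strata nor blocks.
- **Recording.** "Type of surgical procedure" is an item under Demographic data in MEASUREMENTS. Children are scheduled for surgery and evaluated the day before, and envelopes are opened in theatre, so the planned operation is known before allocation.
- **Size and test.** "The minimum total hypothesized sample size of 60 eligible study participants will be needed" for the FLACC objective, and the sentence that follows reads "Taking into consideration an effect size of 20%, significance level of 5% and power of 8-% using Chi Square Test". No other test is named for FLACC. The RESULTS section commits only to accepted statistical methods in general terms.

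**The concern.** Operations on the lower abdomen may differ in how much they hurt afterwards. If they do, the type of operation is a prognostic factor that is known before allocation and already collected, but the protocol gives it no role in the list or in the test it names.

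There are two consequences. With about 30 children per arm, the arms can differ by chance in operation mix, which makes a single trial result harder to interpret. The variation between operations also stays in the error term, so the comparison is less precise than the collected data allow. The allocation part matters more at protocol stage, because a later SAP can add a stratum to the analysis but cannot stratify a list already in use.

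**Working it through.** **1. The plan's own figure.** Inputs from the sample size paragraph: total 60, effect 20%, alpha 5%, power printed as 8-% (read here as 80%), chi-square. The scale of the 20% and the group rates are not given. Read as a 20-point difference, two-sided, the total needed is 70 for 20% vs 0%, 164 for 40% vs 20% and 194 for 60% vs 40%. The figure of 60 is not reproduced; that is a separate matter. What counts here is that 30 per arm has power 0.75 for 20% vs 0%, but only about 0.34-0.39 for mid-range rates.

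**2. Chance imbalance in operation mix.** Assumption: a share p of 30-50% of children have a more painful operation. The documents give no operation mix. A 20-point imbalance is 6 children of 30.

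- *Independent arms:* P(|X1 − X2| ≥ 6) with X1, X2 ~ Binomial(30, p).
- *Fixed 30/30 arms:* with K = 60p such children in total and X in one arm (hypergeometric), P(|2X − K| ≥ 6).

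| p | K | Binomial | Hypergeometric |
|---|---|---|---|
| 0.3 | 18 | 0.120 | 0.158 |
| 0.4 | 24 | 0.147 | 0.187 |
| 0.5 | 30 | 0.155 | 0.196 |

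**3. Validity.** Simulated trials of 30 per arm, yes/no outcome, rates of 30% and 70% in the two operation groups (assumption), no treatment effect: the type I error of the plain chi-square is about 0.05 with the more painful group at 30% or at 50% of children.

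**4. Precision.** Same setting, with rates 20 points lower in one arm (10% and 50%), plain chi-square against Cochran-Mantel-Haenszel (CMH) by operation group:

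| Share of more painful group | Plain chi-square | CMH | Gain |
|---|---|---|---|
| 30% | 0.38 | 0.44 | 0.06 |
| 50% | 0.35 | 0.40-0.41 | 0.05-0.06 |

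*Hand check at a 50% share.* The overall rates are 0.5 and 0.3, so the variance sum is 0.25 + 0.21 = 0.46. The part between operation groups is 0.5 × 0.5 × 0.4² = 0.04 per arm, which leaves 0.46 − 0.08 = 0.38 within groups.

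- Unadjusted: 0.20/√(0.46/30) = 1.615, power Φ(1.615 − 1.96) = 0.37.
- Stratified: 0.20/√(0.38/30) = 1.777, power Φ(1.777 − 1.96) = 0.43. The gain is about 6 points.
- With a 20-point gradient (40% and 60%), the between part is 0.5 × 0.5 × 0.2² = 0.01 per arm, so the within-group sum is 0.44: 0.20/√(0.44/30) = 1.651, power 0.38. The gain is about 1 point.

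**5. If the list is also stratified.** With arms balanced within operation groups, CMH has simulated power 0.44 and 0.41, against 0.36 and 0.33 for the plain chi-square on the same list, a gap of about 8 points. The plain test then becomes conservative (type I error about 0.035). A stratified list should therefore be paired with a stratified analysis.

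**The case against.** The other side has a good case, and much of it stands.

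- *Unstratified randomisation is a legitimate design.* This stands. A reader might infer that an imbalance in operation mix biases the block comparison: 20 points of imbalance times a 40-point gradient is 0.20 × 0.40 = 8 points, or 40% of a 20-point effect. But such an imbalance can fall either way, has probability 0.12-0.20 under the assumptions, and is already covered by the test's error rate. The figure also reads the undefined 20% as percentage points.
- *The protocol does not fix chi-square as the primary analysis.* This stands. It is named only for the sample size, and covariates are commonly left to the SAP. The analysis half of this point is therefore advice on what to prespecify. The allocation half is set in the protocol itself.
- *Nothing in the documents ranks operation type as a cause of pain differences.* This stands. A reader might call it the main known source of variation, but the protocol gives no FLACC or rescue data by operation. It can be treated only as a plausible prognostic factor that is already recorded.
- *Heterogeneity is limited in other ways:* one hospital, ages 2-7, ASA I-II, elective surgery only, one operator for all blocks. This is true, but none of these limits restricts the operation within the lower abdomen.
- *Gains expressed in standard deviations from a linear model would look larger.* They depend on an assumed explained variance and do not describe a chi-square or CMH test, so they are not relied on here.

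**Conclusion.** The point holds as a suggestion to consider. The planned comparison is unbiased and keeps its type I error. It leaves operation mix to chance, with probability about 0.12-0.20 of an imbalance of at least 20 points if 30-50% of children have a more painful operation. It also gives up about 5-6 points of power for a 20-point effect if rates differ by 40 points between operation groups, and about 1 point if they differ by 20. The shares and gradients are assumptions, because the documents give neither. The gain would not make up for the low power at 30 per arm, so this is no remedy for the sample size. It is worth doing because it costs little and the variable is already collected.

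**What to change.** 1. Define two operation groups in advance, three at most, based on the planned operation.
2. If the allocation list is not yet in use, stratify it by these groups with small permuted blocks. This also serves the stated aim of equal groups: with independent even/odd numbers, an exact 30/30 split has probability only 0.10. The protocol describes randomisation in the past tense, so the sponsor should first say whether the list exists.
3. In either case, state that FLACC will be compared with operation group as a stratum or covariate: CMH if the score is dichotomised, van Elteren or a linear or ordinal model if it is kept as a score.

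**Cost.** A few lines of text and a list with two or three strata; no new data. The groups must be fixed before enrolment, and strata may end with incomplete blocks. Because the protocol replaces children whose block fails, replacements would have to be drawn from the same stratum's list.
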